We will recruit 8 blind subjects between the ages of 7 and 18 from the UPMC Eye Center patient population, the Wicab website, the established volunteer list of over 200 blind subjects from the Sensory Substitution Laboratory, the Clinical Trials Registry at the University of Pittsburgh and the patient population at the ophthalmology department at the UPMC Children's Hospital. Recruitment of normally sighted controls is not justified. We expect to screen 15 blind subjects to achieve our enrollment target. Based upon estimates from our preliminary data, this sample size should allow us to show differences between the naïve and BrainPort condition with a significance level of p<0.05 and a power of greater than 0.8.

We will attempt to enroll an equal number of males and females to the extent this is possible. We will attempt to enroll minority populations in our study.

Inclusion Criteria

Volunteer subjects enrolled and treated in this study must meet all of the following criteria:

- 1. Between the age of 7 and 18
- 2. Blind (documented visual acuity of light perception or worse) in both eyes from an eye care provider.
- 3. Able to read (or have read to him or her), understand and sign the Informed Consent and Assent form.
- 4. Able to understand the training and rehabilitation protocols involved in the study.
- 5. Willing to use the BrainPort device

Exclusion Criteria

Subjects will be excluded from the study if they meet any of the following criteria:

- 1. Current oral health problems as determined by the subject's history, and an examination of the oral cavity performed by a member of the study team. Subject is excluded if any of the following conditions are met:
 - a. A history of injury to the tongue resulting in impaired sensation or use of the tongue.
 - b. Visible open lesions, cold sores, abrasions, blisters, or rash on the tongue.
 - c. Oral surgery or dental work in the past 3 months or anticipated to occur for the duration of participation in the study (does not include routine dental health exams/cleanings).
 - d. Piercing on the tongue.
 - e. Performance better than 20/5000 on the FrACT acuity test (same visual criteria as FDA safety study).
- 2. Known neuropathies of tongue or skin tactile system.
- 3. Unwilling or unable to adhere to all study requirements, including completion of the training period, evaluation tests and follow up visits.
- 4. Implanted electrical medical devices such as pacemakers.

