- 5. Known allergies to nickel, gold or other components of stainless steel.

Study Duration

The duration will be up to 5 visits over the course of approximately 2 weeks. Study sessions will be limited to 90 minutes in length. A subject can elect to have up to two sessions per day which would reduce the duration of the study. We are requiring that at least one parent or caregiver be present for all study visits.

Study Procedures

Screening and Enrollment

The study will be explained to the potential candidates and their parents, including the purpose, procedures, expectations for participation, benefits, and risks. Upon request, an IRB approved patient information sheet explaining the study can be provided for review at home. If the potential subject shows interest in the study, additional pre-screening questionnaires will be administered to determine eligibility. Specifically, our study coordinator will review the inclusion and exclusion criteria over the telephone. We have included this paradigm successfully in other studies with the Brainport, which reduces the likelihood that a subject will travel to our site at their own expense but not meet our inclusion and exclusion criteria.

If the potential subject has successfully passed our pre-screen tests over the phone, then he or she will be provided by mail with the Informed Consent form and the HIPAA Research Authorization Form, the participant Assent form and the Parental Permission form, which will have been approved by the University of Pittsburgh Institutional Review Board. We will offer to provide a JAWS compatible version and/or an audio version to the subject prior to their arrival so that they can review it at their own pace and with their families. These same documents will be reviewed again with the subject and their family member upon arrival for the initial visit. In the event that the subject is not able to sign their own name, a proxy designated by the subject may provide the signature.

A HIPAA research authorization will allow the researchers to access the subject's medical records related to their diagnoses and to enable further disclosure of the subject's study data to the study personnel, study monitor, clinical research organization, and the IRB.

Overview of Study Design

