Following consent, subjects will complete baseline psychophysical assessments which have been used in similar BrainPort studies. These consist of simple and easy to understand computer based tests of the ability to detect light, direction, motion, and letters. In addition, we may administer seated tests where the subject is asked to recognize objects, pictures or depth cues. Each of these tests takes between 5 and 15 minutes to complete.

Following baseline studies, a structured "Clinical Training Phase" with the will occur. Our lab has trained over 100 subjects to use the BrainPort device (largest center worldwide), and has established the methods to provide core skill acquisition under the direction of an occupational therapist who works in our laboratory (refer to attachment). Because the subjects in this study will not be taking the device home, but will be restricted to limited use in the controlled laboratory setting, the training will not have to involve outdoor navigation or more advanced skills. After the Brainport training phase has been completed, and the subject has demonstrated basic proficiency with the device, the same set of outcomes assessments administered at baseline will be repeated.

If at any point during the study, the subject subsequently does not meet inclusion criteria or satisfies exclusion criteria, or wishes to stop participation, further testing will be discontinued and the subject will be dismissed.

Detailed description of study design by visit:

Session 1:

- Informed consent
- Review of inclusion and exclusion criteria
- Baseline medical and medication history
- Oral exam
- Baseline psychophysical assessments

Session 2, 3, & 4:

- Training session
- Oral exam

Session 5:

- Repeat outcomes assessments with Brainport
- Oral exam

Each session is expected to last 90 minutes, will be performed at the UPMC, and will be performed by the Research Staff and/or PI.

Note: follow up visits can be combined into a single longer day with morning and afternoon sessions at the request of the subject. We are allowing this because subjects and their families are responsible for their own travel, lodging and meal expenses.

Evaluation Procedures/Outcomes Assessments (Detailed descriptions):

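### The protocol leaves open whether a child who is not yet proficient with the device is retested at Session 5; if such children go untested and gain less than the others, the mean gain would tend to be overstated (minor)

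*Combined protocol and SAP*

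**What the plan says.** The Overview of Study Design says that the baseline assessments are repeated "After the Brainport training phase has been completed, and the subject has demonstrated basic proficiency with the device". The visit-by-visit description that follows lists training in Sessions 2, 3 and 4, and for Session 5 gives "Repeat outcomes assessments with Brainport" with no condition.

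On time available, Study Duration states "The duration will be up to 5 visits over the course of approximately 2 weeks". The Training Curriculum says that subjects learn at different rates and that some will need longer on certain skills. It describes checks before moving to the next stage but sets no pass mark for basic proficiency. The skills reached are recorded on the case report form.

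The overview also has a stopping rule: if a subject ceases to be eligible or wishes to stop, "further testing will be discontinued and the subject will be dismissed". Lack of proficiency is not named there.

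Statistical analysis (general) plans pre/post t-tests on all measures in the battery, and the Analysis of Test Results sections add ANOVA. Neither names an analysis set or says what is done with a child who has a baseline but no post-training score. Not every test is fixed for every child: of the object tests the overview says "we may administer seated tests where the subject is asked to recognize objects, pictures or depth cues".

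**The concern.** The within-child change is the only efficacy comparison; there is no control group. Proficiency and the post-training score both reflect how well the child uses the device. If the first decides who gets the second, the children with a score are plausibly those who gained most. Having each child serve as his or her own control does not help, because pairing cannot supply a second measurement that was never taken.

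What is at stake is what the result describes. If everyone is retested, it is the mean gain of the blind children enrolled. If only proficient children are retested, it is the mean gain of those who learned the device, and a reader could not tell which. A score not taken at Session 5 cannot be recovered later.

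**Working it through.** **The plan's own figure.** Subject selection criteria gives 8 children "with a significance level of p<0.05 and a power of greater than 0.8". No effect size, standard deviation, sidedness or number of tests is stated, so this power cannot be reproduced. It can only be turned round: for a paired t-test, two-sided 0.05, one test, 7 degrees of freedom and noncentrality d × √8, a power of 0.80 needs d = 1.156 SD of the gain. This serves below as a yardstick.

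**Bias in general.** With m of 8 children untested, the overstatement is (m/8) × (mean gain of tested − mean gain of untested). It is zero if m = 0, and also zero if the untested gain as much as the rest.

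**Size under stated assumptions.** The documents give neither the number who fail to become proficient nor the relation of proficiency to gain. Assume joint normality, a proficiency-gain correlation ρ of 0.3 to 0.7, and that the least proficient one or two go untested. Then

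shift = ρ × mean of the top k of 8 standard normal order statistics.

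The two lowest expected order statistics for n = 8 are −1.4236 and −0.8522, and all eight sum to zero. So:

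- k = 7: 1.4236 / 7 = 0.2034
- k = 6: (1.4236 + 0.8522) / 6 = 0.3793

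| Untested | ρ = 0.3 | ρ = 0.5 | ρ = 0.7 |
|---|---|---|---|
| 1 of 8 | +0.061 SD | +0.102 SD | +0.142 SD |
| 2 of 8 | +0.114 SD | +0.190 SD | +0.266 SD |

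These shifts do not depend on the true mean gain. Against 1.156 SD they are 5.3% to 12.3% with one untested and 9.8% to 23.0% with two. The protocol also specifies a Bonferroni correction. If that covers four tests (an assumption), the detectable gain is 1.53 SD, and the full range becomes about 4% (0.061 / 1.53) to 17% (0.266 / 1.53).

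**Power.** At a true gain of 1.156 SD, the chance of a significant benefit is:

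| Pairs | Lost at random | Least proficient lost, ρ = 0.3 | ρ = 0.5 | ρ = 0.7 |
|---|---|---|---|---|
| 8 | 0.80 | 0.80 | 0.80 | 0.80 |
| 7 | 0.72 | 0.77 | 0.81 | 0.86 |
| 6 | 0.62 | 0.72 | 0.79 | 0.86 |

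The first column is from the noncentral t distribution; the others are simulated. The marked loss of power belongs to random loss. Under selective loss, the upward bias offsets it partly or wholly, or more than offsets it.

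**Counting untested children as no change.** The bias is (k/8) × shift − (1 − k/8) × true gain. For k = 6:

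- true gain 0: 0.75 × 0.114 = +0.085 SD to 0.75 × 0.266 = +0.199 SD
- true gain 1.156 SD: subtract 0.25 × 1.156 = 0.289, giving −0.204 to −0.090 SD

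This can miss in either direction, so it belongs beside the tested-only result and does not replace it.

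**The case against.** The best reply is that the overview describes a sequence and sets no gate: train, become proficient, retest. The visit list is the more specific text and schedules Session 5 for everyone. The stopping rule does not mention proficiency, and the checks in the Training Curriculum control the next stage of training, not outcome testing. Evaluation Procedures can also be read as still giving the basic tests to a child who sees little with the device. All of this stands. It is why the point is an ambiguity to settle and not an error shown to occur.

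Four stronger readings are tempting but not supported:

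- **That slow learners are dismissed.** A reader might join the stopping rule to exclusion 3, "Unwilling or unable to adhere to all study requirements, including completion of the training period, evaluation tests and follow up visits". That criterion concerns adhering to requirements and completing training. A child who attends Sessions 2 to 4 and learns slowly has done both, so the reading is strained.
- **That each untested child costs power.** This holds if pairs are lost at random. It does not hold in general when the least proficient are lost, which is the case at issue here.
- **That the gain is overstated.** This needs at least one untested child and a lower gain in such children. The first is possible and the second plausible; the documents establish neither.
- **That the harder tests can have no baseline.** Inclusion requires "Blind (documented visual acuity of light perception or worse) in both eyes from an eye care provider", and Evaluation Procedures withholds higher-function tests from anyone who sees no better than that. But that sentence follows one about what the device allows, so it may govern testing with the device; the overview also lists letters among the baseline tests.

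**Conclusion.** The concern holds in a limited form, and its severity is minor. The overview attaches a proficiency condition to the outcome assessment, the Session 5 list does not, and no analysis set or missing-score rule settles the matter. Followed literally, the overview makes measurement depend on learning the device, which would tend to raise the only efficacy comparison if those left out gain less.

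The size cannot be taken from the documents. It is zero if all 8 are tested or all become proficient. The range of +0.06 to +0.27 SD for one or two untested children rests wholly on the assumed correlation, normality and selection of the least proficient. It illustrates the possible scale and does not estimate what happened.

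**What to change.** 1. Reconcile the overview with the Session 5 list, so that every child with a baseline who is still in the study and willing repeats the baseline tests regardless of proficiency. State that slow learning alone is not a reason to withhold outcome testing.
2. Define the primary analysis as all children with a baseline who began training, on the measures given to everyone at both times, and name those measures. Report the number and reason for any child without a Session 5 score. Show a sensitivity result counting those children as no change beside the tested-only result, and only for measures that have a baseline score.
3. Report proficiency descriptively, from the skills already entered on the case report form.

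The cost is mostly wording: Session 5 is already scheduled and skills are already recorded. If the object present/absent task is to be among the common measures, an optional test becomes fixed. With light detection and light localization that makes three tests; at the stated 5 to 15 minutes each, they take 15 to 45 of the 90 minutes. The downside is that the mean effect may look smaller.

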- 4) The BrainPort already has CE Mark approval and pending FDA approval (final safety study documents submitted to the FDA August 2013), and should be available for purchase by 2014, at least in Europe and Canada. Whether the device could be useful in a pediatric population is an important clinical question.
- 5) The relation of the anticipated benefit to the risk presented by the study is at least as favorable to the subjects as that provided by available alternative approaches (blind training).

RESEARCH DESIGN AND METHODS

Primary Efficacy Endpoints

The primary efficacy endpoint for this study is a statistical analysis of subjects' improvement over baseline in any of the following areas: light detection, light localization, movement perception, and standardized object recognition tasks after use of the BrainPort. To test our primary endpoints, we will use a within-subjects repeated measures design.

Statistical analysis (general)

All data will be stored in a password encrypted PASS Statistics version 18 database whose contents will be available only to members of the study team. We will use t-tests to assess the differences in performance for all measures on our assessment battery, pre- and post-training. Bonferoni correction will be used to correct for experiment-wise error rate (*i.e.*, the increased possibility of finding many significant correlations due to the multiple tests conducted). Separate analyses of covariance will be performed using age, sex, education, and years since diagnosis as covariates. The major advantage of this design is subject homogeneity; that is, random subject effects are reduced. Because the subjects serve as their own controls, factors such as age, education, mental status, motivation, and disease are completely matched; thus these factors will not contribute to the main effect of training. Matching is always very difficult in individuals with eye disease, and this design resolves this confound.

Subject selection criteria

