Potential subjects will be examined to verify that vision in each eye is light perception or worse by the PI according to standard practices at the UPMC Eye Center. Subjects will not need to be dilated. In most cases, our blind subjects have prosthetic eyes or have such badly damaged eyes that verification of blindness by clinical exam does not need to occur. In these instances, the ocular examination will be waived. Inspection of the oral cavity, medical and medication history will be performed.

Psychophysical assessments: We begin with rudimentary vision assessment such as light perception and proceed to increasingly complex visual tasks which approach "normal" vision as the device allows. In the event that a subject is not able to perceive better than light perception, tests which ascertain higher functions will not be administered. Below is a representative description of the tests that we commonly employ with BrainPort studies.

The Basic Assessment of Light Motion (BaLM) and Basic Assessment of Grating Acuity (BaGA) have been developed with the intent of testing artificial vision devices, which provide the most rudimentary visual precepts. They have been used to quantify such qualities as light detection, temporal resolution and light motion as well as "grating acuity" for situations where standard resolution acuity is nonexistent. The methods for testing have been described in Artificial Vision by Mark Humayan. Both tests run on a software platform and are presented on a computer LCD screen to the subject. The stimuli they present consist mainly of large targets of varying patterns. The subject is seated in a regular chair while looking at a computer display for these non-invasive tests, each of which last an average of 10 minutes or less. The subject is able to stop the test in the event they feel they need to get up and move around. All visual acuity measurements will be performed by a single examiner. For baseline testing, while one eye is tested, the other will be occluded. We use this to make sure that both eyes have visual acuity of LP or worse to meet entry criteria. Subsequent testing using the Brainport is done using the camera pointed at the computer screen. All vision tests will be performed in a room with standardized illumination.

BaLM Test

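### The stop rule for higher-function tests conflicts with the entry criterion and the pre/post design: depending on when it is applied, primary-endpoint pairs are either missing or selected on outcome

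*Combined protocol and SAP*

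**What the plan says.** All references are to the combined protocol and SAP.

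- **Primary Efficacy Endpoints.** The endpoint is improvement over baseline in any of "light detection, light localization, movement perception, and standardized object recognition tasks after use of the BrainPort", and to test it "we will use a within-subjects repeated measures design". Statistical analysis (general) compares pre- and post-training performance by t-tests.
- **Inclusion Criteria, item 2.** "Blind (documented visual acuity of light perception or worse) in both eyes from an eye care provider".
- **Overview of Study Design.** On the baseline assessments: "These consist of simple and easy to understand computer based tests of the ability to detect light, direction, motion, and letters". On object tests: "In addition, we may administer seated tests where the subject is asked to recognize objects, pictures or depth cues". After training, "the same set of outcomes assessments administered at baseline will be repeated".
- **Evaluation Procedures/Outcomes Assessments.** Testing starts with light perception and moves to harder tasks as far as the device permits. Then comes the stop rule: "In the event that a subject is not able to perceive better than light perception, tests which ascertain higher functions will not be administered". On the unaided eye tests: "For baseline testing, while one eye is tested, the other will be occluded". Later testing with the BrainPort points the camera at the screen.
- **BaLM Test.** Only the light and location modules are used.
- **Analysis of Test Results (BaLM/BaGA and object recognition).** ANOVA compares performance before and after BrainPort use.

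The stop rule does not name a session, does not say whether perception is judged unaided or with the device, and does not define higher functions. No passage says how a test that was not given is scored or analysed.

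**The concern.** The rule's condition, vision no better than light perception, is the entry criterion restated. A child who fails to meet the condition unaided is not eligible. If staff apply the rule at Session 1, it applies to everyone and the higher tests are withheld from the whole sample. The post-training battery is defined as the set given at baseline, so those tests drop out of Session 5 as well. If staff instead apply it only at Session 5 with the device on, whether a child contributes a pair depends on how well the device works for that child.

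The endpoint is a within-child change in 8 children, with no control group. Which tests are given, and to whom, decides what the trial can estimate. A baseline not taken before training cannot be recovered afterwards.

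**Working it through.** **1. The plan's own figure.** The plan does not say how many children will have a pair in each area. The nearest figure is under Subject selection criteria: 8 children, p<0.05, power above 0.8. It cannot be reproduced, because no effect size or SD is given. Inverting the paired t-test (8 pairs, 7 df, noncentrality dz × √8, where dz is mean change divided by SD of change), 80% power needs dz = 1.16 at two-sided 0.05. With Bonferroni over the four named areas (0.05/4 = 0.0125) it needs dz = 1.53. Both assume all 8 pairs exist.

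**2. Rule applied at the unaided Session 1.**
- Entry criterion: light perception or worse in both eyes.
- Condition for withholding: not better than light perception.
- Every eligible child therefore meets the condition, 8 of 8.
- Pairs for a withheld test: 8 − 8 = 0, so it has no pre/post comparison.

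| Primary area | Effect of the rule at Session 1 |
|---|---|
| Light detection | Not affected; it is the starting test |
| Light localization | No pairs if it counts as a higher function; the text does not say |
| Movement perception | Separate gap: the BaLM motion module is not used and no other motion test is described |
| Object recognition | No pairs if withheld; separately, the Overview of Study Design already makes object tests optional |

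**3. Rule applied only at Session 5, with the device.** Let a fraction p of children pass and gain G1 on average, and let the rest gain G0. The paired analysis reports G1. The mean over all children is p × G1 + (1 − p) × G0. The overstatement is (1 − p) × (G1 − G0), which is positive whenever children who fail would gain less.

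Illustration with assumed figures: children who pass reach 60% on localization, and everyone else stays at chance, as all do unaided. Chance is 100/8 = 12.5% for eight directions and 100/4 = 25% for four; the Light Localization section allows either.

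| Children passing | Directions | Reported gain | Mean over all 8 | Overstatement |
|---|---|---|---|---|
| 4 of 8 | 8 | 60 − 12.5 = 47.5 | 4 × 47.5/8 = 23.75 | 23.75 |
| 6 of 8 | 8 | 47.5 | 6 × 47.5/8 = 35.6 | 11.9 |
| 7 of 8 | 8 | 47.5 | 7 × 47.5/8 = 41.6 | 5.9 |
| 4 of 8 | 4 | 60 − 25 = 35 | 4 × 35/8 = 17.5 | 17.5 |

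**4. Loss of pairs.** With 4 pairs instead of 8, df falls from 7 to 3 and the two-sided 5% critical t rises from 2.36 to 3.18, before any Bonferroni adjustment. Holding dz at 1.16, power is 0.80 with 8 pairs, 0.62 with 6 and 0.36 with 4. That describes pairs lost at random. When loss depends on outcome, dz among the remaining children may be larger, so the main harm is bias.

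**The case against.** The strongest reply is that the plan clearly intends baseline testing above light detection. The Overview of Study Design says children complete tests of direction, motion and letters at baseline, and the analysis sections presuppose pre-training values. Confirming that an eye is no better than light perception, and applying the FrACT exclusion, also imply some unaided testing above that level. The sentence before the stop rule ties progression to what the device allows, so the rule may concern aided performance only. The BaLM and BaGA are described as made for the most rudimentary percepts, so localization need not be a higher function.

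Most of this stands. A reader might infer that every primary area beyond light detection has no baseline, or that three of the four areas are lost to this rule. The documents do not support that. They contradict each other on which tests are given, the localization claim depends on an undefined term, and movement perception and the optional object tests have gaps of their own.

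The device-aided reading does not resolve the problem, because it leads to step 3 of the working and also breaks the promise to repeat the baseline set. It is fair to add that Session 5 follows demonstrated basic proficiency, so half the children staying at chance is a severe assumption; the table shows the bias shrinking as more children pass.

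One could also compare Session 5 scores with the known chance level of a forced-choice test. The plan does not specify this, and a child with residual light perception might score above chance unaided, so the baseline should be measured.

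**Conclusion.** The concern holds as an internal conflict with consequences for the primary endpoint. The stop rule cannot be reconciled with inclusion criterion 2, the baseline battery, the repeat of that battery and the pre/post analyses.

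- **At the unaided Session 1:** 0 of 8 pairs for any primary test classed as a higher function. That covers object recognition, and light localization on one reading.
- **Only with the device at Session 5:** pairs exist only for children who do well with it, and the mean gain is biased upward. The size is unknown. The figure of 47.5 against 23.75 points rests on an assumed 60% score and an assumed half of the children staying at chance. The direction rests only on poorer device users gaining less.

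The loss of baselines is conditional, because neither the occasion nor the term is defined. It would be too strong to say that the design cannot measure these areas. It can, if the tests are given to all children at both sessions, and the protocol does not secure that.

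**What to change.** In Evaluation Procedures/Outcomes Assessments, replace the stop rule with wording such as:

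> *Light detection, light localization and the object present/absent task are given to every child at Session 1 (unaided) and at Session 5 (with BrainPort), whatever the result on simpler tests. The stop rule applies only to tests outside the primary areas.*

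Then:

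- Change the optional wording for object tests in the Overview of Study Design to match.
- Use the same number of directions for localization at both sessions.
- If a started test cannot be completed, keep the child in the paired analysis with the chance score for the format used: 50% for two-choice, 25% for four directions, 12.5% for eight. A fixed score understates variability in a sample of 8, so add a sensitivity analysis that excludes such scores.

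The missing motion test, and the separate success requirement before the 3- and 5-object tasks, need their own decisions; this change does not settle them.

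The cost is a wording change and a few extra minutes of near-chance testing per child at baseline. The protocol puts each test at 5 to 15 minutes. No new equipment or staff are needed.
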